3.2.3. Exploratory Outcome Measures

Fluorescence microscopy

Samples will be imaged using fluorescence microscopy and ICG cellular locality assessed. Assessment of the margin with fluorescence microscopy will be compared to assessment of the margin with standard H&E staining and fluorescence intensity correlated to the margin reports.

Fluorescence mapping

Intra-operative fluorescence mapping images will be analysed and fluorescence intensity of areas of interest measured. The fluorescence intensity will be correlated to the histopathology reports to create fluorescence mapping algorithms to improve the interpretation of the fluorescence intra-operatively in subsequent studies.

3.3. Outcomes

3.3.1. Primary Outcome

The pathology report of the resected tumour will provide a margin status. The percentage of patients with unexpected positive margins will be calculated for each group to give the unexpected positive margin rate. This will then be compared between the two groups as described in section 10.2.1.

3.3.2. Secondary Outcomes

The length of index operation and type and frequency of adjuvant and neo-adjuvant therapies will be compared between FGS and SoC groups on the day of operation. Local/regional/distal recurrence and difference in overall survival will be compared between the two groups at the 12-month time point. The number of complications and length of hospital inpatient stay will be compared between the two groups at day of operation and at 1-, 6- and 12-month follow-up time points. EQ-5D-5L/EQ-5D-Y scores and TESS/pTESS scores we be compared between the two groups at every follow up time point.

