Population	intermediate to high-grade bone or	soft tissue sarcoma suitable for		
	curative resection.			
Planned Sample Size	Total n=500 (FGS with ICG n=250, S	tandard Care n=250)		
Planned Number of	Up to 20			
Sites				
Intervention Duration	12–24-hour time period between t	ne administration of intravenous		
	(IV) ICG and the start of the resection.			
Follow Up Duration	Patients will be followed up for 12 months following the procedure,			
	with the option of an additional time point at 5 years if further funding			
	is secured.			
Planned Trial Period	58 months (7 months setup, 30 mo	nths of recruitment, 3 months		
	surgical delay, 12 months follow up	, 6 months final		
	report/dissemination)			
	Objectives Outcome Measures			
Primary	To determine whether FGS using	The UPM rate, defined as the		
	ICG reduces the UPM rate	percentage of patients with an		
	compared to the current standard	unexpected positive margin, will		
	of care (SoC).	be compared between the two		
	treatment arms.			
Secondary	Complications	Rates of intra- and postoperative		
	complications as recorded in the			
	clinical notes.			
	Length of index operation Difference in length of operation			
	in minutes.			

TRIAL SUMMARY

	Length of inpatient stay	Difference in length of inpatient stay in days.			
	Perceived impact of intervention in surgical decision making	The percentage of operations in which the surgeon stated FGS changed their planned resection.			
	Local recurrence (LR) rate	The difference in rate of local recurrence at 12 months.			
	Regional/distal recurrence rate	The difference in rate of regional/distal recurrence at 12 months.			
	Overall survival (OS) rate	The difference in rate of overall survival at 12 months.			
	Identify rates of adjuvant and neo-adjuvant therapies	Rates of adjuvant and neo- adjuvant therapies as per clinical notes.			
	Quality of life (QoL) measurements	The difference in scores on EQ- 5D-5L/EQ-5D-Y.			
	Recovery following resection	The difference in scores on the Toronto extremity salvage score (TESS)/ Paediatric Toronto extremity salvage score (pTESS)			
Exploratory Objectives	To determine the role of ICG in the pathological margin assessment of resected sarcoma specimens	Fluorescence microscopy to assess extracellular and cellular ICG spatial orientation in tumour tissue versus surrounding normal tissues			

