2. RATIONALE

During evidence synthesis for this trial, we found some variability in reported negative versus positive margins rates from centres around the UK. Furthermore, the definitions of margin status can be misleading. Statements in the literature regarding 'planned positive margins' are not helpful. Expert sarcoma surgeons understand the concept that a 'planned positive margin' is usually acceptable in terms of not undertaking a further resection because the margin is at a critical structure such as a major nerve or blood vessel. However, a 'planned positive margin' is not always positive- it may be negative, albeit close to the tumour. Therefore, for the purposes of this trial the terminology for margins post-surgery based on the pathology report of the resected specimen will be as follows:

- Negative margin: with the closest distance to the tumour measured in millimetres
- Unexpected positive macroscopic margin
- Unexpected positive microscopic margin
- Acceptable positive macroscopic margin
- Acceptable positive microscopic margin

In November 2020, the National Cancer Research Institute Sarcoma Research Group (UK) reached a consensus that trials in surgery are a priority to assess new technologies that may improve surgical performance.³¹ To date there have been no randomised sarcoma trials with a surgical intervention. Recently published case series data suggested that the use of FGS using ICG for high grade sarcoma resection may reduce the UPM rate.³² As such, undertaking this randomised control trial of FGS in sarcoma is well-timed. This trial will be exclusive to sarcoma patients, but inclusive of all ages and subtypes except low grade sarcomas because they do not fluoresce. Delivery of this trial will provide the sarcoma community, nationally and internationally, with crucial insights into performing more effective surgery, the opportunity to develop improvements to the current standard surgical and histopathological techniques, answers to questions on functional outcomes and the optimal timing of adjuvant therapies. With UPMs clearly linked to inferior oncological outcomes in the short term (e.g., decreased time to local recurrence) and longer term (e.g., poorer overall survival), this randomised surgical trial represents an important step towards improving these outcomes for sarcoma patients.

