3.1.2. Secondary Objective(s)

To determine the effect of FGS using ICG compared to the SoC over a 12-month period on the following areas:

- o Complications
- Length of index operation
- Length of inpatient stay

- Perceived impact of the intervention on surgical decision and change in surgeon preference throughout the trial
- Local recurrence
- Regional/distal recurrence
- Rates of adjuvant and neo-adjuvant therapies.
- Overall survival
- Quality of life (QoL)
- Recovery following resection

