3.2.2. Secondary outcome measures

Complications

Complications may be split into both intraoperative and postoperative. Intraoperative complications could include:

- Blood loss requiring transfusion
- Inadvertent damage to nerves
- Inadvertent damage to tendons/ligaments
- Inadvertent damage to bony structures
- Myocardial infarction
- Stroke
- Other events determined by the PI to be a complication of the surgery

Postoperative complications could include:

- Wound infection
- Wound dehiscence
- Seroma
- Flap complications
- Deep vein thrombosis
- Pulmonary embolism
- Myocardial infarction
- Stroke
- Other events determined by the PI to be a complication of the surgery

Post operative complications will be graded by the PI at site using the Calvien Dindo Classifications of Surgical Complications ³³. The scale indicates the severity of the complication and the therapy needed to correct the complication. The scale consists of 7 grades of severity (I, II, IIIa, IIIb, IVa, IVb, V). See Section 16.4, Appendix 4 for a table of the Calvien Dindo Classifications of Surgical Complications.

Length of index operation

Length of index operation and length of inpatient stay will be measured in minutes and days, respectively.

Recurrence

Local/regional/distal recurrence is defined as the recurrence of sarcoma at the site of primary resection (local) or at a site other than that of the primary tumour, including distal metastasis. Investigations must be tailored to circumstances but where possible should include histological confirmation.

Therapies

Adjuvant and neo-adjuvant therapy rates will include radiation therapy and/or chemotherapy. The type and frequency of therapy will be recorded.

Survival Status

Overall survival (OS) is defined as death due to any cause. Where possible, the specific cause of death should be documented, allowing the calculation of disease specific survival.

Quality of Life

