7.6. Trial Assessments

Length of index operation and perceived impact of the intervention on surgical decision making will be collected immediately post-surgery. Follow up visits at 1, 3, 6 and 12 months will follow standard of care follow up clinic visits and will be conducted as per standard of care at the treating centre. These visits will include the completion of questionnaires (EQ-5D-5L/EQ-5D-Y and if applicable TESS/pTESS). At the day of surgery, 1-, 6- and 12-months visits serious adverse events and complications, including extra clinic visits and hospital admissions since previous assessment, will be collected. At day of surgery, 1- and 6 month visits adverse events will be collected. At the 6- month visits, information will be collected on margin status, local/regional/distal recurrence, length of inpatient stay, adverse events, and serious adverse events. At the 12-month visit overall survival will be collected. Surgeon preference for the different methods of surgery will be collected throughout the trial.

SarcoSIGHT

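### Section 3.3.2 compares adjuvant therapy on the day of operation, before any can have been given, although section 3.1.2 asks for the effect over 12 months

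*Protocol*

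**What the plan says.** Section 3.3.2 of the protocol assigns a comparison time point to most secondary outcomes. For therapies it says that the "type and frequency of adjuvant and neo-adjuvant therapies will be compared between FGS and SoC groups on the day of operation". It then places recurrence and overall survival at 12 months, and complications at the day of operation and at 1, 6 and 12 months.

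Section 3.1.2 opens its list of secondary objectives with "To determine the effect of FGS using ICG compared to the SoC over a 12-month period on the following areas", and the list includes "Rates of adjuvant and neo-adjuvant therapies".

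Section 3.2.2 defines the measure: "Adjuvant and neo-adjuvant therapy rates will include radiation therapy and/or chemotherapy. The type and frequency of therapy will be recorded". It gives no visit or window. The Trial Summary gives the source, "Rates of adjuvant and neo- adjuvant therapies as per clinical notes", also without a window.

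Section 7.6 sets out what each follow-up visit collects. At 6 months, "information will be collected on margin status, local/regional/distal recurrence, length of inpatient stay, adverse events, and serious adverse events"; at 12 months it adds overall survival. Adjuvant therapy is not named at any visit, and the schedule in section 7.7 has no row for it.

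**The concern.** A comparison fixed at a moment when the event cannot have occurred gives the same answer whatever the treatment does. Anyone who follows section 3.3.2 literally will report no adjuvant therapy in either arm, and that result will say nothing about fluorescence guidance. Anyone who follows section 3.1.2 will look for therapy over 12 months and will find no visit in sections 7.6 or 7.7 that is told to collect it.

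At stake is one declared secondary outcome: whether fluorescence guidance changes how many patients go on to radiotherapy or chemotherapy after surgery. An analysis plan can choose the model and the summary measure. It should not have to decide which of two conflicting protocol time points applies, and it cannot ensure that sites capture the data in a uniform way.

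**Working it through.** No sample size or power figure is involved, so the check sets the protocol's statements side by side.

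**Time point of the comparison**

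- Section 3.3.2: day of operation, for adjuvant and neo-adjuvant therapy together.
- Section 3.1.2: effect over 12 months, for the same item.
- Section 3.2.2 and the Trial Summary: no time point.

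Take the two parts separately, using the ordinary meaning of the terms (neo-adjuvant before the resection, adjuvant after it).

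- *Adjuvant, counted on the day of operation.* With 250 patients per arm, the count is 0/250 versus 0/250 and the difference is 0 − 0 = 0, for any true effect. Section 10.2.2 names logistic regression for binary secondary outcomes. With no events in either arm the odds are 0 in both, and the odds ratio, 0/0, is undefined.
- *Neo-adjuvant, counted on the day of operation.* This can be counted. It is given before the resection that fluorescence guides, so it describes the arms and cannot show an effect of the guidance.

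The stated time point therefore suits the component that the intervention cannot affect, and gives no information on the component that it might affect.

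**Where the data would come from**

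- Section 4.1: eCRFs are completed at baseline, on the day of resection and at 1, 6 and 12 months, so post-operative visits with forms already exist.
- Section 7.6: follow-up content is questionnaires, complications, adverse and serious adverse events, margin status, recurrence, length of stay and survival. Adjuvant therapy is not named.
- Section 7.7: there is no row for radiotherapy, chemotherapy or adjuvant therapy. The nearest row, concomitant medications, is marked once, before surgery. Sections 7.5 and 8.3 limit it to tyrosine kinase inhibitors and immunotherapy.
- Section 8.1.3: after an unexpected positive margin, re-excision plans and results are to be documented. Adjuvant treatment is not mentioned.
- Section 3.2.2 and the Trial Summary: therapy will be recorded, from the clinical notes.

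The protocol thus commits to recording therapy and names a source, but it names no visit or window for the post-operative part.

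**The case against.** The strongest reply is that section 3.3.2 is loosely drafted and does not record a deliberate decision. The same paragraph also places the comparison of inpatient stay at the day of operation, among other times, where it is equally uninformative. Section 3.1.2 already states the intended period, and the clinical notes will contain the treatment whatever the visit lists say. This has force. It supports treating the problem as a contradiction to be corrected, with no need to suppose that the outcome was never meant to be measured. It does not make the day-of-operation wording usable.

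A reader might go further in four ways that the documents do not support.

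- *That the whole outcome is empty.* Only the adjuvant component is; neo-adjuvant therapy can be counted that day.
- *That adjuvant therapy will not be collected.* Silence in sections 7.6 and 7.7 does not prove this, because those lists are incomplete on other items. Re-excision results go on the 6-month eCRF under section 8.1.3, yet neither list mentions them. Recurrence is compared at 12 months, but section 7.6 names it only at 6 months and the schedule has no row for it. The eCRFs and the section 4 flow chart are not in the text available here.
- *That the planning rates size the loss.* Using the rates in section 10.3, 250 × 0.138 = 34.5 and 250 × 0.051 = 12.75 patients would have an unexpected positive margin, a difference of 21.75. That counts margins. The protocol gives no rate of adjuvant therapy by margin status, so the figure does not predict a difference in treatment. Nor does the protocol say how far adjuvant therapy determines 12-month recurrence.
- *That the rationale must be cut.* Section 2 hopes for "answers to questions on functional outcomes and the optimal timing of adjuvant therapies". This is not among the listed objectives, and the time-point error does not depend on it. Whether to keep the phrase is an editorial matter.

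**Conclusion.** The point holds for the adjuvant component. Section 3.3.2 fixes a time point at which that component is 0 versus 0 by construction, and this contradicts the 12-month period in section 3.1.2. Because the rule is stated and gives a wrong result if followed, it is an error in the protocol and not detail left for the analysis plan. The related gap is narrower: recording is promised and a source named, but no visit for post-operative radiotherapy or chemotherapy appears in section 7.6 or 7.7.

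The conclusion rests only on adjuvant therapy being given after the resection. The size of any between-arm difference that would go unseen cannot be derived from the protocol.

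This should be fixed but is not critical. It affects one component of one secondary outcome and leaves the primary outcome, sample size, significance level, interim analysis and safety reporting as they are. Treatment recorded in the clinical notes can still be retrieved.

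**What to change.** In section 3.3.2, give the two components separate time points. Describe neo-adjuvant therapy received up to the day of operation, by arm. Compare adjuvant radiotherapy and chemotherapy received from index surgery to 12 months, as any versus none and by type. This brings the section into line with section 3.1.2.

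In sections 7.6 and 7.7, name adjuvant therapy as an item at the existing 1-, 6- and 12-month eCRF visits, recording type and start date. For patients already followed up, complete these fields from the clinical notes, the source that the Trial Summary already gives.

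The cost is a protocol amendment, a few eCRF fields and some retrospective completion by sites. No new visit is needed, and nothing changes in how patients are treated.

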3.3.3. Exploratory Outcome

Fluorescence microscopy

The outcome will be the identification of ICG cellular locality within resected sarcoma specimens, as well as preliminary evaluation of the role of fluorescence microscopy in the pathological assessment of sarcoma specimens in identifying the tumour margin.

Fluorescence mapping

The outcome will be the production of fluorescence mapping algorithms to aid surgeons with the assessment of fluorescence intra-operatively.

SarcoSIGHT Protocol version 5.0 dated 25 June 2024

4.2. Fluorescence Microscopy

As part of the exploratory analysis, a sub-sample of participants recruited at the lead centre in Newcastle will be selected to have their tissue sample further analysed at the NovoPath Newcastle MRC Node. This sub-sample will include 25 tissue samples from participants who received ICG, along with 25 tissue samples from participants who did not receive ICG acting as controls. Fluorescence microscopy will be used to assess cellular ICG locality versus standard haematoxylin and eosin staining and against our validated sarcoma specific marker matrix metalloproteinase-1 (MT1-MMP), for determining margin depths and distances.

4.3. Fluorescence Mapping

As part of the exploratory analysis a sub-sample of still images from the Stryker SPY-PHI camera used to guide surgery in the FGS arm will be collected from all 250 patients and sent to our collaborators at University College Dublin. Our collaborators will use the images to perform fluorescence mapping and will correlate fluorescence intensity to histopathological margin reports. This information will be used to develop artificial intelligence algorithms with the goal of improving the interpretation of fluorescence intra-operatively.

6. ELIGIBILITY CRITERIA

Patients of all ages with a histological diagnosis of intermediate- to high-grade sarcoma will be eligible for the trial. A patient's eligibility for the trial will be initially discussed during local hospital multidisciplinary team (MDT) meetings. Those patients who are interested in taking part in the trial will have their eligibility status assessed by a clinician who has been formally delegated the responsibility by the Principal Investigator (PI). Eligibility assessment and outcome will be documented in the patient's clinical notes. Please note eligibility assessment is not the same as confirmation of eligibility. Confirmation of eligibility for the trial can only take place after consent to take part in the trial has been given by the patient or the patient's parent or carer.

To be eligible for the trial, all the following inclusion and exclusion criteria must apply.

6.1. Inclusion Criteria

- 1. Patients of any age
- 2. Capacity to provide written, informed consent (or legal guardian if <16 years of age)
- 3. Histologically confirmed diagnosis of intermediate to high grade sarcoma
- 4. Amenable to surgical resection as a part of curative intent for the patient

6.2. Exclusion Criteria

- 1. Due for surgery with palliative intent
- 2. Recurrent tumours
- 3. Intracranial, retroperitoneal, and visceral anatomical locations
- 4. A woman of child bearing potential* who is currently pregnant (as confirmed by urine pregnancy test)
- 5. A woman who is currently breastfeeding
- 6. Known allergy to ICG, iodine, iodine dyes or shellfish.
- 7. Unable to provide written, informed consent
- 8. Patients with hyper-thyroidism or autonomic thyroid adenomas
- 9. Premature infants/neonates with exchange transfusion indication due to hyperbilirubinemia

*For the purposes of this trial a woman is considered of child-bearing potential (i.e., fertile) following menarche and until becoming post-menopausal unless permanently sterile. Permanent sterilisation methods include hysterectomy, bilateral salpingectomy and bilateral oophorectomy. A postmenopausal state is defined as no menses for 12 months without an alternative medical cause. A high follicle stimulating hormone (FSH) level in the postmenopausal range may be used to confirm a post-menopausal state in women not using hormonal contraception or hormonal replacement therapy. However, in the absence of 12 months of amenorrhea, a single FSH measurement is insufficient.

6.3. Other Clinical Considerations

- There is an increased risk of adverse reactions to ICG in patients with increased renal insufficiency. As such ICG should only be administered after a careful risk/ benefit assessment
- The lodine content of ICG can interfere with thyroid tests performed before or after administration of the dye. Therefore, radio-active iodine uptake studies should not be performed at least one week following ICG injection. Clinicians should discuss this with their patients
- Although, anaphylactoid and anaphylactic reactions are very rare with ICG (<1/10,000), a clinician should still be available to respond in an emergency.

NB: Enrolling a patient onto the trial who does not meet the inclusion/exclusion criteria is considered a protocol waiver and is in breach of Regulation 29 (SI 2004/1031) of the Medicines for Human Use (Clinical Trials) Regulations 2004. PROTOCOL WAIVERS ARE NOT PERMITTED as is UK legislation.

7. TRIAL PROCEDURES

7.1. Recruitment

7.1.1. Patient Identification

Most patients treated for sarcoma in the UK are referred to one of the 20 specialist centres in the UK; this may occur either before or after diagnosis, but before definitive surgery. Suitable patients should therefore be identified at a multidisciplinary team (MDT) meeting as soon as a histological diagnosis is made and prior to definitive surgery.

7.1.2. Screening

All patients discussed at the MDT with a new histologically confirmed diagnosis of intermediate to high grade sarcoma should be screened for eligibility. Because the time between diagnosis and surgery tends to be relatively short (i.e., a couple of weeks), it is important that screening is achieved in a timely manner so that patients can be approached, given time to consider the trial and then consented to the trial prior to their surgery.

An electronic screening log on the Sealed Envelope Red Pill database will capture pseudonymised screening data including the following:

• Date of screening

SarcoSIGHT Protocol version 5.0 dated 25 June 2024

- Age of patient at screening
- o Sex of patient at birth
- o Histologically confirmed diagnosis of intermediate to high grade sarcoma
- o Tumour Amenable to curative surgical resection
- Patient interest in taking part (Yes/ No)
 - If no, reason given
- Patient information sheet (PIS)given
- o Date PIS given

